### **Screening for eligibility**

The screening mechanism is the same for both substudies.

Interested individuals will initiate contact with the study team either via the listed phone numbers, emails or by completing the on-line survey requesting more information and granting permission to contact. Interested individuals will be contacted by a member of the research team to describe the study, confirm his/her interest in the study, perform a phone screening, and, if appropriate, schedule evaluation appointments. In the event that the prospective participant cannot be reached or does not return the contact, the research team member will initiate no more than three follow-up attempts. The phone screen assess inclusion and exclusion criteria including the Telephone Adaptation of the Modified Mini-Mental State Exam (Norton et al., 1999).

### **Enrollment**

The enrollment mechanism is the same for both substudies.

Once a person has indicated a desire to participate, we will: 1) work with them to schedule a study visit; 2) enter their name and contact information onto the participant database; and 3) mail a packet of materials. The packet will include an informational cover letter summarizing the program, details on the evaluation appointment (date, time, location, parking instructions, etc.), and instructions for participants to complete the appropriate forms (medical history and current medication list, Patient Questionnaire portion of the UPDRS and the Pittsburgh Sleep Quality Index) and bring the forms to their evaluation appointment. Participants will receive a reminder phone call two days prior to the scheduled study visit. During this call a member of the research team will discuss the informed consent process and any additional questions the person may have about study participation.

### **Baseline**

The baseline assessment is the same for both substudies.

All participants will complete approximately three hours of testing at each testing time point. All testing will occur in the on medication state. Testing will consist of biomechanical, non-motor features and disease severity data from each individual. The following are the specific assessment components for each time point:

**Baseline assessment (or Pre-test for those assigned to the normal care control group)**

- A. Intake and review of forms
  - a. Review Screening measures (completed prior to arrival)
  - b. Consent form
  - c. Demographic data
  - d. Review medical history (completed prior to arrival)
- B. General Questionnaires
  - a. Review current medication list (completed prior to arrival)
  - b. Physical Activity Scale for the Elderly (Washburn et al., 1993)
  - c. Fall history questions
  - d. Activity Specific Balance Confidence Index (Powell & Myers 1995).
  - e. The MacArthur Scale of Subjective Social Status (Adler, Epel, Castellazzo, & Ickovics, 2000)
- C. Clinical measures
  - a. Review Patient Questionnaire section of the UPDRS (completed prior to arrival)
  - b. Movement Disorder Society Unified Parkinson Disease Rating Scale (MDS-UPDRS) (Goetz et al., 2008)
  - c. New Freezing of Gait Questionnaire (Nieuwboer et al., 2009)
  - d. PASS iADL assessment (Chisholm, Toto, Raina, Holm, & Rogers, 2014)
  - e. Canadian Occupational Performance Measure (Law et al, 1998)
- D. Measures of motor function
  - a. Timed Up and Go test (Posiadlo & Richardson, 1991)
  - b. Four square step test (Dite & Temple, 2002)
  - c. Mini-Balance Evaluation Systems Test (mini-BESTest) (Franchignoni, F., et al, 2010)
  - d. Standardized gait analysis – computerized mat (Pilgram, Earhart, & [name], 2016)
  - e. Gait Analysis – free locomotion.
- E. Measures of non-motor function
  - a. Review the Pittsburgh Sleep Quality Index (completed prior to arrival) (Buysse, 1989)
  - b. Beck Depression Inventory-II (Beck et al, 1996)
  - c. UCLA Loneliness Scale V3 (Russell 1996)
  - d. Perceived Isolation Scale (Chisholm et at, 2014)

All selected assessment tools are valid and reliable and have been previously used to assess individuals over the age of 65 years and/or individuals with PD.

**General Questionnaires:**

Demographic, medical history, PD history and current medication data will be collected from each individual. The demographic form will be sent to the individual's home with the welcome letter and the participant will be asked to complete the form and bring it with them to their visit. This information is necessary for the study as it allows for proper categorization of levadopa equivalent dosage levels which may impact symptom presentation and medical history information which may help to inform if the individual is healthy enough for exercise.

The Physical Activity Scale for the Elderly allows for quantification of current exercise and sedentary behaviors.

As falls are one of the primary variable of interest for the larger study, the Fall history questionnaire will provide data on falls in the previous 6 months as well as the most common mechanisms for falls. During the study falls will be logged weekly. Additionally, the Activity Specific Balance Confidence Index will provide data about how fearful individuals are about falling and how this level of confidence changes with various tasks that are common to everyday living.

The effect of socioeconomic status on exercise practices for individuals with PD in rural and metropolitan underserved communities is one of the primary aims of this study. The MacArthur Scale of Subjective Social Status will be used to assess how perceived status and income related to exercise practices.

**Clinical measures:**

The MDS-UPDRS is the gold standard in clinical rating of disease severity for individuals with PD. All individuals in study 1 will complete this assessment at all assessment points. The assessment will be administered by a trained investigator. Additionally, all UPDRS subsection III components will be recorded for blinded rating by a study team member blinded to the testing session.

New Freezing of Gait Questionnaire – is a valid and reliable tool for rating the presences of motor freezing during gait for individuals with PD. All individuals in study 1 will complete this assessment at all assessment points.

The Performance Assessment of Self-care Skills (PASS) assessment (Chisholm, Toto, Raina, Holm, & Rogers, 2014) will be administered to examine changes in performance of activities of daily living. The PASS consists of 26 activities of daily living and is designed to allow for a client-centered, performance-based means of objectively assessing occupation-based interventions. Additionally, this kitchen component of the PASS assessment will be performed in an instrumented environment (SMIL kitchen) to allow for quantification of kinetic and kinematic measures relative to the performance of these tasks.

The Canadian Occupational Performance Measure (COPM) will be administered to assess the participant's self-report of performance and satisfaction of self-selected occupational tasks.

**Measures of motor function:**

The Timed Up and Go test and Four Square Step Test are common clinical measures of motor function. Both tests have been used in elderly populations and individuals with PD to examine the effects of interventions and have been found to have a high degree of reliability and validity when used in the listed population groups.

The mini-BESTest will be used to assess balance. This 14-item, clinical battery is used to assess balance in four component areas (anticipatory transitions, postural response, sensory orientation and dynamic gait) and provides a single number summary of balance performance (maximum possible score = 30). This is relatively commonly used balance assessment battery. Mini-BESTest performance will also be video recorded for rating by a blinded rater.

Standardized gait analysis – Using the GaitRite® System, we will capture the temporal and spatial parameters of each participant during walking. The GaitRite® mat is a 14 foot portable electronic walkway, embedded with sensors to enable the measurement spatiotemporal variables of gait such as cadence, normalized velocity, stride length, base of support, and percent of cycle in double support. Participants will begin at a starting point two meters from the mat, then walk toward and step onto the mat to continue walking until they achieve the stop line located two meters off of the opposite side of the mat. Data will be collected for forward preferred speed, backward preferred speed, forward fast, tandem and dual task gait. Each participant will complete five trials for each condition.

Free locomotion gait analysis - Additional gait data will be collected during free locomotion, that is walking that is not constrained by a specific task or area. Participants will be asked to walk throughout the laboratory space and through nearby ground-floor hallways outside the laboratory, while wearing miniature wearable sensors to record their motion. These sensors are approximately 50mm square by 20mm thick. They are mounted with straps to the tops of the shoes, and optionally the ankles, thighs, waist, upper arms and lower arms. Sensors record time, acceleration, angular velocity, magnetic field, air pressure (altitude), and optionally relative distance. Sensors will be worn throughout the duration of each lab visit, to measure movements beyond the range of other instruments. Data obtained concurrently with the in-lab assessments listed above will be used to quantify foot motion with improved detail relative to the other instrumentation.

**Measures of non-motor function:**

Measures of sleepiness and depression will be collected as these are known confounds in both elderly individuals and individuals with PD. The two selected batteries, the Pittsburgh Sleep Quality Index and the Beck Depression Inventory-II are questionnaires that the participants will complete prior to the end of each session.

As depression can significantly impact performance on the outcome measures, influence the extent to which exercise benefits an individual and be improved via exercise, the Beck Depression Inventory will be administered to all individuals. As this tool or the health history form may identify depression or suicidality, a follow-up plan has been established to address both contingencies. The questions that address suicidality will be viewed by the PI within minutes of the completion of the survey tool. However, as little to no evidence exists to suggest that suicide rates differ systematically from the general population, we will not have a clinical psychologist or psychiatrist on the research team.

**Follow-up Plan (Suicidality):** In the event that a participant is identified as being at imminent risk of harm (e.g., suicidal), the PI will immediately assign a study team member to call 911 while the PI remains with the individual. The participant will be notified by the PI that a confidentiality breach has occurred.

**Follow-up Plan (clinically concerning depression):** In the event that a participant scores at or above a 3 on the depression index question that specifically refers to suicide, the PI will notify the study participant of the potential concern and will make a recommendation for further clinical care. This notification will occur in a private area designated for confidential communication such as consent procedures. Only the PI and the participant will be present.

During all testing sessions:

1. **Rest breaks** – Participants will be frequently prompted and given rest breaks regularly and as needed.
2. **Adherence to medication schedules** – As medication management can significantly impact the safety of the individual as well as the outcomes of the data collection sessions, individuals will be instructed to maintain their medication schedules during testing procedures.
3. **Safety protocol during testing** - To minimize risks to participants during evaluation sessions, a spotter to assist in preventing falls will be present as needed and a gait belt can be donned as necessary. Testing staff will also be prepared to provide first aid for minor injuries and to contact emergency healthcare personnel in the event of a more serious injury. In the event of a more serious, life-threatening emergency, the emergency protocol described below will be implemented.

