Frustration: Participants may become frustrated with the assessments as the complete battery may take up to 3 hours to complete.

Embarrassment: Individuals may be embarrassed if they are unable to perform a task or if they stumble or fall during the performance of a task.

**Suicidality:** The identification of suicidal thoughts is possible due to the depression questionnaire. In the case of identified suicide risk, the study team will immediately call 911. This will compromise the confidentiality of the participant and the participant will be notified of this breach of confidentiality.

- a. **Steps to Psychosocial Risks: Confidentiality:** All possible care will be taken to maintain confidentiality. No subject will be identified in any report or publication. All data will be coded at the time of data collection. All participants will be assigned an identification number prior to data collection and all documents and files will be named using this ID. All data will be stored on computers which will be kept in the SMIL. All data analysis will be performed on computers in the SMIL or in the faculty office of the PI. A password is necessary for access to the computers and they all are equipped with automatic log off. Data being moved from one location to another will be moved via UW Box or the College of Education's secure network. Only members performing research have access to these computers, therefore identification of any subjects or data is unlikely. Coded data will be kept indefinitely.

Data will be stored/banked for future research projects in a double secured location. In a locked filing cabinet or a password protected computer within a locked room. Coded data will be stored on the School of Education servers indefinitely. It will be used for future research related to exercise studies in the lab. Data may be shared with researchers outside the UW. [name] will be responsible for deciding when/to whom to disseminate coded data, and will work with other researchers if necessary to confirm that they have proper IRB approval/etc., as necessary. Required UW-Madison IRB approval would be obtained prior to the release of any data.

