**Contact information:** Each participant will have a sealed folder which contains their emergency contact information including instructions for the local 911 operator and contact information for an identified contact person. During the scheduled sessions, the research team member will be given access to the participant folder for the duration of the session. The sealed folders marked with the participant names will be kept locked in the PI's research office. These folders are to be unsealed only in the case of an emergency. All folders and their contents will be destroyed once the individual completes the three-month follow-up or if they withdraw from the study.

Personal privacy during testing sessions will be maintained by testing in a private room and limiting the people within the research lab to current employees or students associated with the lab.

**Frustration:** To minimize the risk of frustration with the data collection sessions frequent breaks will be provided as will snacks and water during the testing sessions. Additionally, the testing sequence provides a variety of tasks to complete. If it appears that an individual is becoming frustrated with the given task, that task can be stopped or paused and a different task can be completed without disruption of the data collection session.

**Embarrassment:** The PI and her team all have experience working with individuals at an increased risk of falls. The study team will also talk with the individual to minimize the extent to which they feel embarrassed. We will minimize the likelihood of falling by using proper spotting techniques.

**Depression:** The risk associated with learning that you are depressed or suicidal based on the Beck Depression Inventory score is difficult to minimize. The study team will follow the developed protocol

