- b. Embarrassment: Individuals may be embarrassed if they are unable to perform a task or if they stumble or fall during the performance of a task.
- c. Depression: As a depression screen is included in the study protocol an individual who does not know they are depressed may need to be notified. In the case of identified serious depression, the PI will notify the study participant of the potential concern and will make a recommendation for further clinical care.
- d. Suicidality: The identification of suicidal thoughts is possible due to the depression questionnaire. In the case of identified suicide risk, the study team will immediately call 911. This will compromise the confidentiality of the participant and the participant will be notified of this breach of confidentiality.
- e. *Confidentiality:* All possible care will be taken to maintain confidentiality. No subject will be identified in any report or publication. All data will be coded at the time of data collection. All participants will be assigned an identification number prior to data collection and all documents and files will be named using this ID. All data will be stored on computers which will be kept in the SMIL. All data analysis will be performed on computers in the SMIL or in the faculty office of the PI. A password is necessary for access to the computers and they all are equipped with automatic log off. Data being moved from one location to another will be moved via UW Box or the College of Education's secure network. Only members performing research have access to these computers, therefore identification of any subjects or data is unlikely. Coded data will be kept indefinitely.

Data will be stored/banked for future research projects in a double secured location. In a locked filing cabinet or a password protected computer within a locked room. Coded data will be stored on the School of Education servers indefinitely. It will be used for future research related to exercise studies in the lab. Data may be shared with researchers outside the UW. [name] will be responsible for deciding when/to whom to disseminate coded data, and will work with other researchers if necessary to confirm that they have proper IRB approval/etc., as necessary. Required UW-Madison IRB approval would be obtained prior to the release of any data.

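### The triggers for the emergency-call response and the recommend-care response to suicidality and depression differ between the protocol's assessment section, its risk section and the DSMP.

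*Combined protocol and SAP*

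**What the plan says.** **Protocol, Measures of non-motor function.** Two headed follow-up plans are given.

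- The Suicidality plan applies to a participant "identified as being at imminent risk of harm (e.g., suicidal), the PI will immediately assign a study team member to call 911". It gives no questionnaire item or score.
- The plan for clinically concerning depression applies to a participant who "scores at or above a 3 on the depression index question that specifically refers to suicide". The response is that "the PI will notify the study participant of the potential concern and will make a recommendation for further clinical care", in private, with only the PI and the participant present. No emergency call is mentioned.

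The section also says that the PI looks at the suicidality answers within minutes and that the team will include no clinical psychologist or psychiatrist.

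**Protocol, Steps to Minimize Risks during Exercise, and the Safety/Emergency Protocols, Psychosocial Risks.** The Suicidality entry says: "The identification of suicidal thoughts is possible due to the depression questionnaire". It continues: "In the case of identified suicide risk, the study team will immediately call 911". Confidentiality is then compromised and the participant is told so.

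**DSMP (Appendix IV), 3.7, Psychosocial Risks.** Item d repeats the Suicidality entry. Item c, on depression, reads: "In the case of identified serious depression, the PI will notify the study participant of the potential concern", followed by a recommendation for care. It does not mention the suicide question.

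**Depression paragraphs closing both risk sections.** On the risk of learning from the Beck score that one is depressed or suicidal, each says only: "The study team will follow the developed protocol".

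**The concern.** These rules tell the team what to do, within minutes, with an answer on a questionnaire. The two responses differ in kind. One is a private conversation with advice to seek care. The other is an emergency call that discloses the participant's state to others.

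The sections attach these responses to different triggers: imminent risk, identified suicide risk, a score on one item, and serious depression. No section defines how these relate.

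An error is possible in both directions. An emergency response that the risk section and the DSMP require might not be made, or confidentiality might be breached where the assessment section provides for a private conversation. With no mental-health specialist on the team, the written rule carries more of the decision.

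**Working it through.** The plan states no figure to reproduce on this point. The check is a comparison of text, followed by a count of questionnaire administrations.

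**Triggers and responses side by side**

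| Place | Trigger for the 911 call | Trigger for notify-and-recommend |
|---|---|---|
| Protocol, Measures of non-motor function | Imminent risk of harm, with suicidal as the example; no item or score | Score of 3 or more on the suicide question |
| Protocol, Psychosocial Risks | Identified suicide risk, with the questionnaire named as a source of suicidal thoughts; no imminence condition, no score | None stated in the list of risks |
| DSMP 3.7, items c and d | As in the protocol's Psychosocial Risks | Identified serious depression |
| Depression paragraphs closing both risk sections | None stated | None stated; reference to a developed protocol |

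**Applying the rules to one case: a score of 3 or more on the suicide question**

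1. Under the assessment section, this score is the stated trigger for notification and a recommendation. The 911 plan applies only if the participant is also judged to be at imminent risk. No item, score or step is given for that judgement.
2. Under the risk section and DSMP item d, the questionnaire can identify suicidal thoughts, and identified suicide risk leads to an immediate call. If the score counts as identified suicide risk, the response is the call.
3. Under DSMP item c, notify-and-recommend belongs to serious depression, so the suicide-question score is not assigned there.
4. The reference to the developed protocol adds no trigger and no order of precedence.

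Step 2 depends on one reading: that a score of 3 or more on a question about suicide is suicide risk identified by the questionnaire. It is the plain reading, because the sentence just before the 911 rule names the questionnaire as the source. It remains an inference, since neither the risk section nor the DSMP mentions the item or a score.

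**Ceiling on exposure**

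Inputs: planned enrolment of 20 per group in Study 1 and 12 in Study 2. The inventory is completed at baseline, posttest and 3-month follow-up, and also at pre-test for the wait-list group.

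- Study 1: 20 × 3 + 20 × 4 = 140
- Study 2: 12 × 3 = 36
- Total: 140 + 36 = 176

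This assumes full enrolment and no dropout. The Power and Statistical Analysis section expects attrition of about 15-20%. Suppose, as an assumption, that this rate holds in both studies and that every dropout leaves after the first visit. There are 20 + 20 + 12 = 52 first visits and 176 − 52 = 124 later ones, so the count is 52 + 0.80 × 124 ≈ 151 to 52 + 0.85 × 124 ≈ 157.

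These are administrations of the questionnaire. The documents give no rate at which participants reach the trigger, so the number of occasions on which the rules would diverge cannot be derived.

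**The case against.** The strongest defence is that the plan already has two tiers. The assessment section says that it provides for both depression and suicidality, and gives each its own headed plan. DSMP items c and d have the same structure. The entries in the risk sections can be read as short descriptions that defer to the headed plans, and the reference to a developed protocol supports that. The two plans are also not exclusive: a participant with a score of 3 who is judged at imminent risk still falls under the 911 plan. Finally, the assessment section puts both decisions with the PI, which limits the chance that different staff act on different sections.

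Much of this stands. Two tiers are stated, and a reader who infers that the documents flatly contradict each other on a named item score goes too far, because only the assessment section names the item. Nor do the risk section and the DSMP say that every degree of suicide risk leads to a call; their wording is identified suicide risk, without a qualifier in either direction.

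The defence does not settle where the suicide-question score belongs. The risk section and DSMP item d drop the imminence condition. The DSMP gives a different trigger for the recommendation. No text says that the headed plans take precedence.

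**Conclusion.** The point holds as an inconsistency of triggers across the protocol's assessment section, its risk section and the DSMP. The divergence in response is conditional: it arises if a score of 3 or more on the suicide question is identified suicide risk. Even without that reading, two differences remain on the face of the text. The imminence condition appears in only one of the three places that require a 911 call, and the trigger for recommending care is the suicide question in the protocol but serious depression in the DSMP.

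Exposure is at most 176 questionnaire administrations. A reader might take that as the number of occasions on which the rules conflict; the documents do not support this, because the rules apply only when a participant reaches a trigger.

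This is a participant-safety matter. It has no bearing on sample size, power or error rates. The change should be made. Which response is right is a clinical question and is not judged here.

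**What to change.** Reconcile the two follow-up plans under Measures of non-motor function, the Suicidality entry in the protocol's risk section, and items c and d of DSMP 3.7 into one text, and use it unchanged in both the protocol and the DSMP. The text should:

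- state the trigger for each response, and how imminent risk, identified suicide risk, clinically concerning depression and serious depression relate to one another;
- state where the suicide-question score falls;
- replace the reference to a developed protocol, in both documents, with a pointer to that text.

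The choice of rule is for the investigator and the IRB. The direct cost is an amendment to the wording of both documents. If the rule chosen needs a step to separate imminent from other risk, that step would be an added procedure, so the cost may not be wording alone. Outcomes and analyses are unaffected.
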